### Standard Treatment

As there is no specific treatment for COVID-19, standard assessment and treatment is based on organ supportive therapy such as oxygen therapy (central), fluid therapy, antibiotic therapy for secondary infections. If the disease progress to severe acute respiratory failure, the patients will often require referral to an intensive care unit for mechanical ventilation.

## Proactive Prophylaxis With Azithromycin and Chloroquine in Hospitalised Patients With COVID-19 (ProPAC-COVID)

In addition, Danish national guidelines for handling of in-hospital Covid-19 patients can be obtained from [www.lungemedicin.dk](http://www.lungemedicin.dk) or from the open access journal European Respiratory Clinical Journal (at present in press).

### 3.3.2. Allocation:

The sponsor generates a randomisation sequence. Randomisation will be in blocks of unknown size and the final allocation will be via an encrypted website (REDCap), where also inclusion and exclusion criteria are required to be filled in correctly in order to randomise a patient.

Allocation will be stratified for age (>70 years vs. <=70 years), site of recruitment and whether the patient has any of the following chronic lung diseases: COPD, asthma, bronchiectasis, interstitial lung disease (Yes vs. No).

### 3.3.3. Data collection, surveys and follow-up:

The primary daily project management is carried out by the project manager. In addition, a project group (investigators), consisting of doctors from the departments involved, is trained to assist the project manager with the recruitment, sampling and follow-up of patients. All medical decisions regarding patients will be taken by a physician. Data is collected in Case Report Forms (CRF) for each individual patient.

Prior to consent to participate in the trial, we will only assess the specific information needed to assess inclusion and exclusion criteria. No other information will be accessed.

It is the attending physician who asks if patients are interested in hearing more about the trial. If yes, an investigator is contacted, who will inform the patient about the trial.

As part of the study, all patients will be regularly monitored for oxygen saturation, heart rate, blood pressure, respiratory rate and temperature during hospitalisation.

The following information will also be obtained:

- Date of birth, age and gender
- Height, weight and BMI
- Use of medicine
- For patients with chronic obstructive pulmonary disease (COPD) classification in GOLD 1-4 and GOLD A-D (symptoms assessed via MRC degree)
- Systematic screening for co-morbidities
- Smoking history with pack years, current smoking status and alcohol consumption
- Information from the chest x-ray
- Arterial-blood gas analysis (pH, pCO2, pO2, Base Excess, oxygen supplementation)
- Hb, leucocytes + differential count, CRP, kidney function, liver parameters, electrolytes, LDH
- ECG, vital status, and adverse events

And from the patients' medical journal:

## Proactive Prophylaxis With Azithromycin and Chloroquine in Hospitalised Patients With COVID-19 (ProPAC-COVID)

\*The blood samples include haemoglobin (Hb), leukocytes + differential count, thrombocytes, C-reactive protein (CRP), Na+, K+, albumin, creatinine, urea, amylase, alkaline phosphatase, beta-2-Microglobulin, fibrinogen, glucose, TSH, INR, bilirubin, D-dimer, APTT, calcium, triglycerides, ferritin and lactate dehydrogenase (LDH). These blood tests will also be recommended daily for COVID patients outside studies in the recommendation of the Danish lung medicine association. \*\*When screening for the study, any ECG from within the last 3 days can be used. \*\*\*A follow-up ECG can be recorded during any remaining days of the hospital admission. \*\*\*\*Only in patients with COPD.

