### **Hydroxychloroquine:**

Categorized as an anti-inflammatory and anti-malaria agent.

The drug is approved and marketed in Denmark for the prevention and treatment of malaria, for the treatment of rheumatoid arthritis, discoid and systemic lupus erythematosus and juvenile idiopathic arthritis.

Manufacturing, packaging and labelling of IMP:

The trial drugs (IMP) are manufactured by Glostrup pharmacy by pharmacist [name]. Placebo capsules are thus made similar to the intervention medicine. The drug (and Placebo) are labelled, according to Appendix 13. Glostrup pharmacy has a key for blinding. Therefore, it will always be possible to unblind a patient if indicated. Investigator must notify sponsor on grounds if a patient is unblinded.

Medical professionals dispense the IMP daily during hospitalization, except for patients preferring to handle their medication themselves. In the latter case, patient will fill in a medication diary (provided at randomisation). For all patients who are discharged during the intervention period, a medication diary will be provided. The medication diary is subsequently collected.

Exactly the amount of medication or placebo that the patient is required to take during the study periode will be provided, but for patients who do not take all the medication (protocol deviation), the remaining medication will be collected by the study staff. The patient will receive a follow-up phone call to check whether they have adhered to the medication schedule according to the trial protocol.

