## Proactive Prophylaxis With Azithromycin and Chloroquine in Hospitalised Patients With COVID-19 (ProPAC-COVID)

Follow-up is done on days 14, 29, 90 and 365 days, by accessing the electronic medical record system. The specific information obtained, and its purpose can be found in section 3.3.3.

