### Regarding other treatment with antibiotics:

If antibiotic therapy is deemed indicated to the patient due to e.g. pneumonia or if it becomes standard therapy, piperacillin-tazobactam should be given as an empirical treatment at a dose adjusted to renal function. In case of penicillin allergy, cefuroxime is also given at a dose appropriate to renal function, weight and age. When positive microbiology is available, immediately switch to targeted treatment.

If *specific suspicion of atypical pneumonia* is raised, ciprofloxacin is administered at a dose of corresponding to kidney function and concomitant examination for atypical pneumonia will be performed. If negative, ciprofloxacin is discontinued. If positive, ciprofloxacin treatment is continued for the duration of treatment corresponding to the microorganism detected. If there is a specific need for treatment with macrolide and where other options are not available (e.g. allergy to fluoroquinolones, or when there is an estimated need for combination treatment of e.g. legionella pneumonia), consult with an investigator, and in this case it may be decided to discontinue azithromycin (active) or azithromycin placebo. In this case, treatment stops without unblinding.

Furthermore, ECG recordings during the treatment period will be analysed with focus on QTc. At QTc (F) > 480/470 ms for respectively women and men, IMP will be discontinued for safety reasons (but the patient remains in the study).

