### 3.3.6. Sample size:

#### Randomised controlled study

Prerequisite: Type 1 error rate = 5%. Power = 80%. Two-sided statistics. Group sequential design with one scheduled interim analysis after randomisation of 113 patients (50% recruitment).

Analysis: T-test.

Sample size is calculated based on the following estimates and indicative figures:

Expected duration of hospitalisation with COVID-19: 10 days

SD for "Days alive and discharged within 14 days" in patients with lung disease and COVID-19: 4 days (up to 10 days hospitalization)

Estimated time for improvement/deterioration: 1.5 days.

This requires 226 patients randomised 1:1 with 113 in each group. This is a fixed sample size. It is assumed that most patients complete the intervention.

However, for interim analysis, the Data and Safety Monitoring Board (DSMB) may recommend the steering committee to expand sample size.

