## **5. Blood samples:**

As part of usual care, blood samples are taken daily from the time of inclusion and as long as the patient is admitted. Blood samples include haemoglobin (Hb), leukocytes + differential count, thrombocytes, C-reactive protein (CRP), Na+, K+, albumin, creatinine, urea, amylase, alkaline phosphatase, beta-2-Microglobulin, fibrinogen, glucose, TSH, D-dimer, APTT, calcium, triglycerides, ferritin, bilirubin, ALAT, INR, and lactate dehydrogenase (LDH), see Table 1. These blood samples are analysed at the hospitals.

In addition, supplemental blood tests and material obtained with nasal swabs will be performed according to the sub-study protocols. Material from this will be included in a research biobank for the trial, and after completion of the trial in another regional biobank. The trial is expected to end in February 2021, and the material will then be transferred to the regional biobank.

For the present trial, the results of blood tests are collected from the patient record.

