- ECG: Qtc: n (%) patients in both arms who at any time point after baseline had a QTc (F) >500 ms
- N (%) ventricular arrhythmias (apart from ventricular extrasystoles and non-sustained VT).

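### Dosing and event recording run to day 15, but no ECG, blood test, vital-sign check or active adverse-event enquiry is described after discharge, so harms are under-ascertained in whichever arm leaves hospital earlier

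*Protocol*

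**What the plan says.** **Treatment and recording window.** Protocol 3.3.4 gives both drugs to day 15. The text on manufacturing, packaging and labelling of the IMP provides a diary for patients who go home during that period and adds: "The patient will receive a follow-up phone call to check whether they have adhered to the medication schedule according to the trial protocol". Protocol section 6 has events recorded from the first dose through day 15. A later sentence in the same section ends recording when the trial drug stops.

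**QTc.** Under the heading on other antibiotic treatment, "ECG recordings during the treatment period will be analysed with focus on QTc", and study drug is discontinued above a threshold.

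**Planned observation.** On the ECG, a Table 1 footnote says "A follow-up ECG can be recorded during any remaining days of the hospital admission". On laboratory tests, section 5 says "blood samples are taken daily from the time of inclusion and as long as the patient is admitted". Section 3.3.3 places vital-sign monitoring within the hospital stay.

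**After discharge.** Section 3.3.4 says: "Follow-up is done on days 14, 29, 90 and 365 days, by accessing the electronic medical record system".

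**Limits on what is recorded.** Section 6 restricts recorded side effects to those absent from the product summaries. It also excludes prolonged admission, re-admission, ventilation and death from the SAE definition.

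**Analysis.** The SAP's arrhythmia items report the number and percentage of "patients in both arms who at any time point after baseline had a QTc (F) >500 ms". No denominator rule and no allowance for the number of ECGs or days observed is given.

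**The concern.** The treatment is meant to shorten hospital stay, and most of the described means of seeing harm exist only during that stay. Ascertainment of harm is therefore tied to the efficacy outcome. If one arm goes home earlier, it has fewer days on which an abnormal blood test, a bedside finding or a reported symptom can reach the trial, although its dosing period is the same length.

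The stakes are cardiac in particular. The protocol excludes patients with a long QTc and stops drug for it, so the safety comparison ought to be even-handed between arms. The section 6 limits add to the problem. QT prolongation is in the protocol's own side-effect lists for both drugs, and syncope and arrhythmia are listed for azithromycin. A non-serious case, even if noticed, may therefore not be recorded as a side effect. A home event that leads to re-admission may not be handled as an SAE.

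**Working it through.** **1. The plan's own figure.** Protocol 3.3.6 gives "Type 1 error rate = 5%. Power = 80%. Two-sided statistics", an SD "in patients with lung disease and COVID-19: 4 days", and a difference of 1.5 days. By the normal formula, n per arm = 2 × (1.96 + 0.842)² × 4² / 1.5² = 111.6, so 112 (224 in total). The exact two-sample t-test gives 112.6, so 113 per arm and 226 in total. The stated 226 reproduces and is not affected by this point. It confirms that 1.5 days is the planning difference used below.

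**2. Share of dosing days after discharge.** Inputs: 15 dosing days (3.3.4); expected stay 10 days (3.3.6); median stay 10–15 days (dosage rationale in 3.3.4); up to 48 hours in hospital before inclusion (3.3).

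Share = (15 − in-hospital days after randomisation) / 15.

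| Total stay | 0 days before inclusion | 1 day before | 2 days before |
|---|---|---|---|
| 10 days | 5/15 = 33% | 6/15 = 40% | 7/15 = 47% |
| 12.5 days | 2.5/15 = 17% | 3.5/15 = 23% | 4.5/15 = 30% |
| 15 days | 0% | 1/15 = 7% | 2/15 = 13% |

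A 4-day spread around a mean of 10 days after randomisation (gamma or normal, assumed) gives about 35%, so averaging over patients changes little. The SAP's expectation of at least 4 days alive and out of hospital within 14 days points the same way: 4 days at home, plus day 15 if also at home, is 5/15 = 33%.

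**3. Difference between arms.** Assume the 1.5 days is entirely earlier discharge.

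- 10-day stay, randomised on day 1: 8.5 v 10 in-hospital days. 8.5/10 = 0.85, so 15% fewer; home share 43% v 33%.
- 10-day stay, two days before inclusion: 6.5 v 8. 6.5/8 = 0.81, so 19% fewer; home share 57% v 47%.
- 15-day stay: 13.5 v 15 (10% fewer), or 11.5 v 13 (12% fewer).

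**4. What that could do to a comparison (illustration).** Assume a constant daily risk h = 1 − (1 − p)^(1/15), where p is the true 15-day risk, and detection only in hospital, so that the observed risk over d days is 1 − (1 − h)^d. With p = 10% in both arms, the observed risks are 5.80% v 6.78% (8.5 v 10 days; ratio 0.85) or 4.46% v 5.46% (6.5 v 8 days; ratio 0.82). For p from 2% to 30% the ratio lies between 0.81 and 0.87, although the true ratio is 1.0. A true 15% v 10% (ratio 1.5) would appear as about 1.24–1.30. This is a limiting case, because some home events would still reach the trial.

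**5. How far this applies to ECGs.** Table 1 is not in the available text. Its footnote is permissive and speaks of one follow-up ECG. If only one is planned, the number of ECGs does not scale with length of stay. Steps 3 and 4 then describe blood tests and bedside observation rather than QTc. Home days would still have no planned ECG, and a patient discharged early might have none after baseline.

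**The case against.** **The missing table.** The ECG schedule and the timing of adverse-event collection may be in Table 1, and section 3.3.3 lists ECG and adverse events among the data obtained. This stands. The point can be made only about the text that is available.

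**Home days are not blank.** A reader might infer that home dosing is unmonitored, or that the QTc rule cannot operate there. The documents do not support that. The diary, the call, record reviews on days 14 and 29, and the 24-hour reporting duty for serious events all continue. The rule can act on any ECG taken in the period, for example at re-admission. What is missing is any planned measurement that would reveal a silent QTc change, and the day-14 review comes before the last dose.

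**The call.** Its stated purpose is adherence, but nothing says other questions are excluded, and its timing is not given. It may already fall at the end of dosing.

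**Event-free by default.** A reader might infer that patients without a follow-up ECG will be counted as having no QTc event. The SAP does not say so. It promises the percentage missing for each variable and the percentage followed for each predefined outcome. That would probably expose missing ECGs, but it would not equalise opportunity between arms.

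**Direction.** It is tempting to say that harm is hidden in the active arm. That follows only if the active arm goes home earlier. Protocol 3.3.6 allows for improvement or deterioration, and if the active arm stays longer the bias reverses. The 1.5 days is also a difference in days alive and out of hospital, so part of it could be deaths or re-admissions.

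**Contradiction.** The ECG footnote and the QTc paragraph do not strictly contradict each other. The latter covers ECGs that are recorded in the treatment period and does not promise them throughout. What is unstated is how the two apply together after discharge.

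**Conclusion.** The point holds in this form: dosing and event recording extend to day 15, while the described ECG, blood tests and vital signs are tied to the admission, and no active adverse-event enquiry after discharge is described. Whichever arm is discharged earlier will have its harms observed less completely.

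The size depends on the stay. At the sample-size assumption of 10 days, 33–47% of dosing days lie after discharge; at 15 days, 0–13%. A 1.5-day difference in discharge removes 15–19% of in-hospital days in the earlier arm at a 10-day stay, and 10–12% at 15 days. These are planning averages derived here; the documents state no such share.

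The conclusion assumes that Table 1 adds no post-discharge assessment and that the 1.5 days reflects discharge timing. It does not establish that the active arm will have fewer ECGs, nor that its QTc events will be under-counted. The primary efficacy analysis and the sample size are untouched.

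**What to change.** 1. **Protocol, data collection.** Time the planned phone call at the end of the dosing period for every discharged patient, and ask the same adverse-event questions in both arms, including syncope and palpitations. At the day-29 record review, record arrhythmias and serious events from home dosing days. This must be reconciled with section 6, which limits recording to side effects outside the product summaries, ends recording when the trial drug stops, and does not treat re-admission or death as SAEs. Without that, the answers may have nowhere to go.
2. **SAP, arrhythmia items.** Keep the number and percentage of all randomised patients. Add by arm: the number with no post-baseline ECG, ECGs per patient, and in-hospital dosing days per patient. Add a supportive comparison at the first follow-up ECG among patients who have one, noting that this subset is selected after randomisation and depends on length of stay. For that reason it cannot be the sole analysis.
3. **Protocol, QTc text.** The sponsor should state how the Table 1 ECG footnote and the QTc paragraph apply together after discharge. No ECG schedule or stopping rule is proposed here.

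The cost is a few questions on a call already planned, one CRF page and some extra tabulation, with no additional visit. The limit is that silent QTc prolongation at home would still go undetected.

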### 3.3.4 Intervention

Neither patients nor study staff will know which group the patient is allocated to. The medicine will be marked neutral, e.g. "Azithromycin group A" and "Azithromycin group B" and the same for Hydroxychloroquine.

NOTE: If the patient is receiving azithromycin prophylaxis, common practice is followed: the prophylaxis is paused and then restarted as usual.

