## **4. Interim Analysis and Data and Safety Monitoring Board**

After recruiting half the sample size (approximately 113 patients), an interim analysis will be performed focusing on safety. An external Data and Safety Monitoring Board is appointed.

The interim analysis will be prepared and presented by physician [name]. The groups will be presented as "Group A" and "Group B" and DSMB will only be unblinded if they ask the steering committee for the study on this.

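### As the protocol describes it, trial drug carries one of two shared group letters, so one code-break decodes every label for anyone who learns of it

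*Protocol*

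**What the plan says.** Protocol section 3.3.4 (Intervention) sets the aim: "Neither patients nor study staff will know which group the patient is allocated to". It then gives the marking: "The medicine will be marked neutral, e.g. 'Azithromycin group A' and 'Azithromycin group B' and the same for Hydroxychloroquine". Under its control group heading, controls receive placebo for both drugs.

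The manufacturing and labelling text under the protocol's introductory Hydroxychloroquine heading adds four things:
- Label detail is deferred: "The drug (and Placebo) are labelled, according to Appendix 13". That appendix was not supplied.
- The code is held outside the trial team: "Glostrup pharmacy has a key for blinding".
- Individual code-breaks are foreseen: "Therefore, it will always be possible to unblind a patient if indicated". The investigator must tell the sponsor the grounds.
- Health professionals dispense the drug daily in hospital, unless a patient prefers to handle it.

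Section 3.3.2 (Allocation) has REDCap make the allocation, stratified by age, site and chronic lung disease, and says of the sequence: "Randomisation will be in blocks of unknown size". Section 4 presents the interim results to the DSMB under the letters A and B. The SAP (Blinding of the statistician) uses arms A and B for the final analysis and says that these are random names. It also gives the interim analysis to someone who is not an investigator of the trial.

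**The concern.** A neutral label hides the drug name but, in the form described, still states the group. Everyone who handles the drug can see which patients belong together. Such a blind holds only while nobody knows what either letter means. Once one patient's treatment is known, that patient's letter is decoded and the other follows by elimination. Past and future patients are then unblinded to whoever has that knowledge and sees their labels.

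The primary endpoint, days alive and out of hospital within 14 days, depends on when staff discharge a patient. ICU admission and non-invasive ventilation are clinicians' decisions too. Knowledge of the arm could shift all three, and could affect who is approached next. A lost blind cannot be restored later in the trial.

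**Working it through.** **Number exposed.** Protocol section 3.3.6 states 226 patients, 113 per group (difference 1.5 days, SD 4, two-sided 5%, power 80%). The normal approximation gives 2 × (1.960 + 0.842)² × 4² / 1.5² = 111.6, so 112 per group. The exact t-test gives 112.6, so 113 per group and 226 in all. The figure reproduces and is used below only as the number of patients at risk.

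**What one code-break reveals.** There are strictly four labels, A and B for each drug. Because controls take placebo for both, decoding one drug's letter gives the arm.
- Shared letters: up to 226 of 226 allocations, for a person who knows of the break and sees the labels.
- Patient-specific numbers: 1 of 226.

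This comparison needs no assumed rate.

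**How likely a code-break is.** The documents give no unblinding rate, so p per patient is an assumption. P(at least one) = 1 − (1 − p)^n. A site is taken as 226 / 8 ≈ 28 patients, from the eight centres stated in the SAP Introduction and assuming equal recruitment.

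| Assumed p | One site, n = 28 | Interim, n = 113 | Whole trial, n = 226 |
|---|---|---|---|
| 0.5% | 13% | 43% | 68% |
| 1% | 25% | 68% | 90% |
| 2% | 43% | 90% | 99% |

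For example, 1 − 0.99^28 = 1 − 0.755 = 0.245, and 1 − 0.99^226 = 1 − 0.103 = 0.897. The site column applies if knowledge of a break stays at the site, and the trial column if it reaches every site.

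**Recognition by side effects (supporting only).** Protocol section 6 lists abdominal pain and nausea as very common (above 10%) for both drugs. It gives no placebo rate, so the rates below are assumed. With m patients per letter, the chance that the letter with more events is the active one is P(X_active > X_placebo) + ½ P(tie), for two independent binomials. About 28 / 2 = 14 per letter is a whole site, and 7 is half-way through its recruitment. Judging one patient alone, without shared letters, is right with probability ½ + (p_active − p_placebo) / 2.

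| Active vs placebo | 7 per letter | 14 per letter | Single patient |
|---|---|---|---|
| 10% vs 5% | 62% | 68% | 52.5% |
| 15% vs 10% | 60% | 65% | 52.5% |
| 20% vs 10% | 69% | 77% | 55% |
| 30% vs 10% | 82% | 91% | 60% |

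These are rates of a correct best guess, not of knowing the code.

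**Predicting the next allocation (secondary).** If visible letters show the balance within a block, guessing the letter that is behind (a coin toss when level) is right 71% of the time for blocks of 4 and 68% for blocks of 6, by enumerating all sequences, against 50%. These block sizes are assumptions.

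**The case against.** The strongest reply is that the premise is not established. The marking is only an example, and the governing label text is in an appendix that has not been seen. A pharmacy key and the unblinding of a single patient fit patient-level coding as well as group letters. This stands as a limit on wording: the point concerns the scheme as described, and it cannot be said that all supplies carry only a letter. It does not remove the point. A number printed beside a group letter would not help, and if the appendix uses unique numbers without letters, section 3.3.4 is wrong and needs correction.

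A reader might infer that one code-break unblinds the whole trial. The documents do not support that. The investigator reports the grounds to the sponsor; nothing says that the allocation is circulated to other sites. The protocol also provides ways of stopping drug without a code-break: section 3.3.4 covers a need for macrolide treatment and QTc stops, and section 6 lets the treating physician discontinue. The 90% figure is therefore the upper end, for knowledge that reaches every site.

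A reader might also infer that side effects alone would give the code away. Section 6 says that only side effects not already in the product summary are recorded, so known non-serious effects would have to be counted informally. The 91% needs both a large assumed difference and a fully recruited site.

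Predicting the next letter biases recruitment only if its meaning is known or believed. Recruiters would also have to follow each site by age by lung-disease stratum, about 226 / 32 ≈ 7 patients each.

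Finally, the letters in the interim report might seem to be those on the labels. No text says so, and the SAP already uses random names for the final analysis. The protocol simply does not say that the interim letters are separate.

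**Conclusion.** The point holds for the marking as section 3.3.4 describes it. Shared letters turn a code-break meant for one patient into disclosure of up to 226 allocations to anyone who learns of it and sees the labels; patient-specific numbers would confine it to one. That contrast follows from the scheme itself. The chance of its happening does not: about 25% at one 28-patient site and 90% trial-wide at 1% per patient, or 13% and 68% at 0.5%, all resting on an assumed rate and, for a site, on equal recruitment over eight centres. Side-effect pooling is a weaker and gradual route, and block prediction is secondary. Neither is needed for the conclusion. The documents do not show that the blind would be lost across the trial, or that the interim letters match the labels. This is a cheap improvement to the blinding, with one matter to confirm in Appendix 13. It leaves the sample size and the analysis unchanged.

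**What to change.** In protocol section 3.3.4 and on the Appendix 13 labels, replace the group letters with a unique kit or randomisation number per patient. REDCap issues the number, only the pharmacy's list links it to active drug or placebo, and each code-break is made per patient. If Appendix 13 already works this way and prints no group letter, correct section 3.3.4 to match.

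In protocol section 4, add one sentence saying that the interim letters are random names unrelated to any label, as the SAP already says for the final analysis.

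The cost is a change of label text, a kit list at the pharmacy that already makes the capsules and holds the key, and a REDCap field. The downside is that stock must be tracked by kit number instead of by two bulk codes per drug. No further patients are needed.
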